cardiac events.²⁷ Doses of 25 Gy have been shown to induce temporary perfusion defects and ≥ 5 -6% of the heart receiving ≥ 25 -27 Gy has been accepted by some to define “unfavorable cardiac anatomy” based on correlation of this heart volume to the Stockholm trial for patients with left sided tumors that showed a high rate of cardiac morbidity and mortality.^{15, 21-22, 28-29} There is emerging data that doses to specific parts of the heart, such as the coronary arteries, may be more important in predicting cardiac outcomes.³⁰ Strain echocardiogram has recently shown promise as an accurate and relatively inexpensive study to determine myocardial abnormalities in the left ventricle for doses > 3 Gy immediately post radiation and at 2 months following radiation.³¹ Control patients receiving right sided radiation did not show any changes on post radiation studies. Pericarditis is a very rare toxicity, occurring in $<1\%$ of patients, but may lead to hospitalization.³² In addition, the increased use of cardiotoxic chemotherapy over the past several years adds yet another confounding factor to determining the effect of radiation therapy on cardiac outcomes. Doxorubicin and Herceptin, particularly when used in combination, are known to increase the risk of cardiac disease.³³⁻³⁴ These agents were not included in the chemotherapeutic regimens used in the aforementioned trials. Currently, Doxorubicin and Herceptin are both included in standard chemotherapeutic regimens and are often administered in combination.³⁵ It is not fully known how radiation therapy in the setting of these agents will affect cardiovascular outcomes. Maximal cardiac sparing achieved through proton therapy has the potential to decrease this risk by decreasing mean heart dose as well as volume receiving 40 Gy and 25 Gy (Figure 2 & 3).

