5.1 Pre-treatment Criteria

- 5.1.1 Diagnostic Imaging: Patients with lymph node involvement must have a metastatic work up that includes Computed Tomography(CT) scan of the chest, abdomen and pelvis and bone scan or Positron Emission Tomography (PET)/CT scan.
- 5.1.2 Cardiology: Echocardiogram including Strain echocardiogram will be performed for all patients. Echocardiogram data will be collected prior to radiation therapy (or within first week of treatment), within 4 weeks after completion of radiation therapy, and 2 months after radiation therapy.
Echocardiography: Conventional two-dimensional (2D) and Doppler echocardiography will be obtained in standard views. Tissue Doppler imaging will be acquired using standard views. Imaging parameters will be optimized and the frame rate will be set greater than 150 frames/sec for acquisition of tissue Doppler imaging. Echocardiographic loops of at least 3 beats will be recorded. Echocardiograms will be read in the conventional manner and reported in the subject's medical record. TDI-derived parameters, such as myocardial velocities, strain, strain rate and torsion, will be analyzed offline using customized computer software (EchoPac, GE Healthcare, Milwaukee, WI).
- 5.1.3 Pathological review of surgical specimen at the Massachusetts General Hospital or other DF/HCC institution.
- 5.1.4 Complete History and Physical Examination
- 5.1.5 CBC with differential. TSH at baseline. Biomarkers will be obtained with baseline routine labs and in follow with routine labs at 2 additional follow up visits (at 4 weeks after radiation therapy and 2 months after radiation therapy): Approximately 5 cc of blood will be taken for each measurement of BNP and NTproBNP, and 5 cc of blood for ultrasensitive troponin. Blood will be spun at 3000 rpms for 10 minutes, the plasma aliquotted into daughter tubes and stored at -80. BNP levels will be measured with a twosite dual-monoclonal immunochemiluminescent assay (ADVIA Centaur® BNP, Bayer Diagnostics, Tarrytown, NY) using the ADVIA Centaur immunoassay system. NT-proBNP levels will be measured with an electrochemiluminescence sandwich immunoassay (Elecsys® ProBNP, Roche Diagnostics Inc, Indianapolis, IN) using the Roche 2010 system. For non acutely dyspnic subjects aged <75 years of age, the upper limit of normal is considered 125 pg/ml (manufacturers recommendations). Troponin I will be measured using a new generation

CONFIDENTIAL

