7. STUDY CALENDAR

Baseline evaluations are to be conducted within 6-weeks prior to start of protocol therapy. Scans must be done ≤ 12 weeks prior to the start of chemotherapy if delivered or radiation therapy if no chemotherapy is delivered. In the event that the participant's clinical condition is deteriorating, laboratory evaluations should be repeated within 48 hours.

Tests and Observations	Pre-study	During Radiation	Follow Up (1)
Informed Consent and registration	X		
Pathology Review (DF/HCC)	X		
Medical History	X		
Physical Exam	X		X
Echocardiogram (2)	X		X(2)
Imaging	X (3)		As clinically indicated
Toxicity/AE Assessment		X weekly	X
Data Sheets			X (4)
Labs (5)	X		X
Optional Photography	X	X	X

Notes:

(1) Follow up schedule is at 4 weeks and 2 months, and 6 months after treatment, then at 12 months and annually to five years after treatment. Labs are only collected at the first two follow up visits (4 weeks and 2 months). Visit window for follow up is +/- 3 weeks for the 4week and 8 week follow up visits, then +/- 6months for the 6month and annual visits.

(2) Echocardiogram including Strain echocardiogram will be performed for all patients. Echocardiogram data will be collected prior to radiation therapy (or within first week of treatment), at 4 weeks after completion of radiation therapy, and 2 months after radiation therapy. Conventional two-dimensional (2D) and Doppler echocardiography will be obtained in standard views. Tissue Doppler imaging will be acquired using standard views. Imaging parameters will be optimized and the frame rate will be set greater than 150 frames/sec for acquisition of tissue Doppler imaging. Echocardiographic loops of at least 3 beats will be recorded. Echocardiograms will be read in the conventional manner and reported in the subject's medical record. TDI-derived parameters, such as myocardial velocities, strain, strain rate and torsion, will be analyzed offline using customized computer software (EchoPac, GE Healthcare, Milwaukee, WI).

(3) Diagnostic imaging required pre-study:

- Baseline mammography prior to surgery
- For patients with lymphatic involvement Computed Tomography (CT) scan of the chest, CT of the abdomen, and bone scan and/or Positron Emission Tomography (PET)/CT scan are required. For patients with low burden nodal disease, these scans are not required.

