12. STATISTICAL CONSIDERATIONS

We propose to enroll a total of 96 patients in three cohorts following the study design indicated in 12.1 to evaluate independently the feasibility of intensity modulated proton therapy (IMPT) and 3D conformal protons following mastectomy or breast-conserving surgery. The separate cohorts will ensure adequate patient numbers for achieving reasonable precision in the assessment of acute, sub-acute and late toxicities associated with each proton technique in the specific population. The accrual goal includes 20% inflation to account for patients unevaluable or lost to follow-up so that adequate precision is maintained for longer-term endpoints. The target accrual has been adjusted based on the observed data among mastectomy patients with at least 6 months follow-up, including the completeness of strain echocardiogram testing.

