12.2 Analysis of Secondary Endpoints

Secondary endpoints of this study will be analyzed as follows:

- 12.2.1 Exact binomial methods will be used to construct 95% confidence intervals for estimating the rates of acute, sub-acute and late toxicities during and after proton radiation to the left chest wall and regional draining lymphatics. The precision provided by a sample size of 26 patients is associated with a maximum half-width of 20%, but the 95% confidence intervals will be narrower in practice, as the observed toxicity rates are expected to be generally low. The same methods will also be used to analyze the post-radiation outcomes of breast reconstruction, including the rates of implant complication, contracture, infection, unplanned cosmetic surgeries.
- 12.2.2 Progression-free survival is defined as the duration from the start of radiation to the date of objective disease progression or death due to any cause, whichever is earlier. Progression-free survival will be estimated using Kaplan-Meier methodology. The 5-year

CONFIDENTIAL

This document is confidential. Do not disclose or use except as authorized.

progression-free survival rate will be reported and a 95% confidence interval for this rate will be calculated using Greenwood's formula. Patients who do not experience a progression and are still alive will be censored at their date of last contact.

- 12.2.3 Data from the strain echocardiogram will be analyzed for each parameter, including myocardial velocity, strain, strain rate and torsion. ANOVA methods will be used to analyze the pre- and two post-radiation measurements, using linear contrasts to test the significance of cardiac function changes over time. Fixed effects may be incorporated to explore subgroup differences defined by patient and treatment factors, for example, dose level.

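### The strain-echo analysis names ANOVA for three correlated scans per patient without a within-patient model or a missing-scan rule, and the timing of the first post-radiation scan is inconsistent

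*Combined protocol and SAP*

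**What the plan says.** Section 12.2.3 covers each strain parameter (velocity, strain, strain rate, torsion) in one method sentence: "ANOVA methods will be used to analyze the pre- and two post-radiation measurements, using linear contrasts to test the significance of cardiac function changes". It adds that "Fixed effects may be incorporated to explore subgroup differences defined by patient and treatment factors, for example, dose level". It does not mention within-patient correlation, incomplete patients or scan dates.

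Section 12 says the accrual target was adjusted "based on the observed data among mastectomy patients with at least 6 months follow-up, including the completeness of strain echocardiogram testing", and that the goal includes 20% inflation for unevaluable or lost patients. No completeness rate is given.

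On timing, Section 5.1.2 places the post-radiation scans "within 4 weeks after completion of radiation therapy, and 2 months after radiation therapy". Note 2 of the Section 7 calendar places them "at 4 weeks after completion of radiation therapy, and 2 months after radiation therapy". Note 1 adds: "Visit window for follow up is +/- 3 weeks for the 4week and 8 week follow up visits". In both sections the baseline scan may be taken "prior to radiation therapy (or within first week of treatment").

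On side, Section 3 states none. Sections 12.1 and 12.2.1 speak of the left chest wall, and Section 2.1 of left post-mastectomy radiation. Section 2.2 reports from a cited strain study: "Control patients receiving right sided radiation did not show any changes on post radiation studies".

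**The concern.** Three scans on one patient are correlated, and some will be missing. Whether the analysis uses the correlation, and whether it keeps patients with an incomplete set, decides how precisely change is estimated. The sentence in 12.2.3 leaves both open.

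Early cardiac effect is a listed secondary objective (Section 1.3.1), and cardiac sparing is part of the rationale (Sections 1.2.1 and 2.3). Section 1.3.1 calls the secondary endpoints descriptive, yet 12.2.3 plans significance tests, generally by cohort (Section 12.1.2), in groups of 26 to 32. At that size an avoidable loss of precision makes an inconclusive result more likely.

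Scan timing matters for the same contrasts. If the first post-radiation scan can fall anywhere from the end of treatment to week 7, depending on which section a site follows, its mean describes no well-defined time.

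**Working it through.** **The plan's own figure.** The documents give no effect size, standard deviation or power for the echo endpoint. The only figure tied to echo completeness is the accrual goal, and it reproduces: 26 × 1.2 = 31.2, rounded up to 32 per cohort; 32 × 3 = 96.

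**Scan windows** (Section 7, note 1, applied to the echo visits at the same times).
- First visit: 4 ± 3 = weeks 1 to 7.
- Second visit: 8 ± 3 = weeks 5 to 11.
- Overlap: weeks 5 to 7, which is 2 of 6 weeks or one third of each window. If 2 months is read as 8.7 weeks, the second window starts at 8.7 − 3 = 5.7 and the overlap is weeks 5.7 to 7.
- Section 5.1.2 allows weeks 0 to 4. A scan before week 1 satisfies 5.1.2 but not the calendar. A scan after week 4 and up to week 7 satisfies the calendar but not 5.1.2.

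**Precision.** The following inputs are assumptions, not figures from the documents: equal variance at each time (set to 1), common within-patient correlation ρ of 0.5 or 0.7, and each scan missing independently with probability m of 0.1 or 0.2. The contrast is 2 months minus baseline, with 32 patients. The number 32 cancels in the ratios.

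*Reading A: complete-case repeated-measures ANOVA.* The share of patients with all three scans is (1 − m)³: 0.9³ = 0.729 (about 23 of 32) and 0.8³ = 0.512 (about 16 of 32). The complete-case variance is 2(1 − ρ) / [32(1 − m)³]. The mixed-model variance comes from generalised least squares, summing the information over all missing-scan patterns with the covariance taken as known.

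| ρ | m | Complete-case variance | All-scan variance | Ratio |
|---|---|---|---|---|
| 0.5 | 0.1 | 0.0429 | 0.0360 | 1.19 |
| 0.5 | 0.2 | 0.0610 | 0.0422 | 1.45 |
| 0.7 | 0.1 | 0.0257 | 0.0218 | 1.18 |
| 0.7 | 0.2 | 0.0366 | 0.0259 | 1.42 |

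On the standard-error scale this is √1.18 = 1.09 to √1.45 = 1.20.

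*Reading B: ordinary ANOVA, scans treated as independent.* The variance of a difference is 2/n, against 2(1 − ρ)/n when pairing is used. The ratio of standard errors is 1/√(1 − ρ): 1.41 at ρ = 0.5 and 1.83 at ρ = 0.7.

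Reading A uses the correlation and drops patients. Reading B keeps patients and ignores the correlation. They cannot both apply.

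**Side** (conditional). If a share q of patients is right-sided with no change, the pooled mean change is (1 − q) times the left-sided one. Take a left-sided change of 0.57 SD of the difference, detectable with 80% power at n = 26 (two-sided 5%, assumed). At q = 10%, pooled power is 71% against 75% for left-sided patients alone; at q = 30%, it is 50% against 63%. The documents give no value for q.

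**The case against.** The strongest reply is that 12.2.3 never specifies ordinary or complete-case ANOVA. Contrasts for change across one pre- and two post-radiation measurements describe a within-patient analysis, and the fixed-effects sentence is compatible with a mixed model. This stands. A reader might infer that the plan wastes data; the text supports only that it does not rule this out. A paired comparison needing only the two scans in the contrast would also lose less than Reading A.

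Second, a reader might speak of known missing scans. Section 12 shows that completeness was weighed, but it gives no rate, and the plan responded by raising the post-mastectomy goal from 58 to 64 with 20% inflation. That also stands. More patients do not, however, settle how incomplete ones are analysed.

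Third, a reader might infer that pooling both sides dilutes the cardiac signal. Right-sided entry is inferred only from the silence of Section 3, against left-sided wording in Sections 2.1, 12.1 and 12.2.1. Patients without reconstruction must meet a heart or LAD dose criterion, so right-sided entry is plausible mainly among those with reconstruction. The no-change premise rests on one cited study. Dilution is therefore possible but not shown; the disagreement between Sections 3 and 12 is real.

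Fourth, overlapping windows do not confuse the order of two scans in the same patient, and contrasts with baseline remain interpretable. This is largely right. Ambiguity remains where only one post-radiation scan exists and falls in weeks 5 to 7. Section 5.1.5 and calendar note 5 tie biomarkers to week 4 and to the echo times, which narrows the timing conflict but leaves 5.1.2 in disagreement.

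Finally, the endpoint is secondary and called descriptive, and no passage plans to present a null result as evidence of cardiac safety. A reader should not attribute that claim to the plan.

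**Conclusion.** The point holds as under-specification with a better method available at almost no cost. The timing conflict and the overlap in weeks 5 to 7 follow directly from the text. The possible loss is a variance ratio of about 1.2 to 1.45 under complete-case analysis, or a standard-error ratio of about 1.4 to 1.8 under ordinary ANOVA, and never both. Both ranges rest on the assumed correlation of 0.5-0.7, and the first also on independent missingness of 10-20% per scan. With an estimated covariance in cohorts this small, the gain from the mixed model would be somewhat less than shown. If the sponsor already intends a mixed model on all scans, there is no loss and only the wording needs changing. The feasibility rule in Section 12.1 does not use echo data and is unaffected.

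**What to change.** 1. In 12.2.3, replace ANOVA with a linear mixed model for each parameter: time as a factor, an explicit within-patient covariance, all available scans, and contrasts of each post-radiation time with baseline. State the missing-data assumption and report completeness at each time point.
2. Assign scans by actual date under a rule written before analysis, including how a single scan in weeks 5 to 7 is classified. Add a sensitivity analysis using actual time since radiation, and identify baseline scans taken after treatment began.
3. Reconcile Section 5.1.2 with Section 7 on the timing of the first post-radiation scan. No new visit window is needed, and one could not apply to scans already done, since enrolment began in August 2011.
4. Reconcile Section 3 with the left-sided wording in Sections 12.1 and 12.2.1. If right-sided patients were enrolled, pre-specify side (or heart dose) by time as a model term and report the left-sided estimate alongside the pooled one.

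The cost is SAP wording and slightly more analysis. No extra scans or patients are needed.

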12.3 Reporting and Exclusions

- 12.5.1 **Evaluation of toxicity.** All participants will be evaluable for toxicity from the time of their first treatment.
- 12.5.2 **Evaluation of response.** Although patients will not have measurable disease at the time of treatment and therefore response is not an endpoint of this study, all patients will be followed for disease recurrence.

13. PUBLICATION PLAN

The results should be made public within 24 months of the end of data collection. If a report is planned to be published in a peer-reviewed journal, then that initial release may be an abstract that meets the requirements of the International Committee of Medical Journal Editors. A full report of the outcomes should be made public no later than three (3) years after the end of data collection.

15. APPENDICES

Appendix A. Performance Status Criteria

ECOG Performance Status Scale		Karnofsky Performance Scale	
Grade	Description	Percent	Description
0	Normal activity. Fully active, able to carry on all pre-disease performance without restriction.	100	Normal, no complaints, no evidence of disease.
		90	Able to carry on normal activity; minor signs or symptoms of disease.
1	Symptoms, but ambulatory. Restricted in physically strenuous activity, but ambulatory and able to carry out work of a light or sedentary nature (e.g., light housework, office work).	80	Normal activity with effort; some signs or symptoms of disease.
		70	Cares for self, unable to carry on normal activity or to do active work.
2	In bed < 50% of the time. Ambulatory and capable of all self-care, but unable to carry out any work activities. Up and about more than 50% of waking hours.	60	Requires occasional assistance, but is able to care for most of his/her needs.
		50	Requires considerable assistance and frequent medical care.
3	In bed >50% of the time. Capable of only limited self-care, confined to bed or chair more than 50% of waking hours.	40	Disabled, requires special care and assistance.
		30	Severely disabled, hospitalization indicated. Death not imminent.
4	100% bedridden. Completely disabled. Cannot carry on any self-	20	Very sick, hospitalization indicated. Death not imminent.

CONFIDENTIAL

This document is confidential. Do not disclose or use except as authorized.

	care. Totally confined to bed or chair.	10	Moribund, fatal processes progressing rapidly.
5	Dead.	0	Dead.

CONFIDENTIAL

This document is confidential. Do not disclose or use except as authorized.

Toxicity CTCAE version 4.0 from <http://ctep.cancer.gov>

Condition	Short Name	Grade 1	Grade 2	Grade 3	Grade 4	Grade 5
Fatigue (lethargy, malaise, asthenia)	Fatigue	Mild fatigue over baseline	Moderate or causing difficulty performing some ADL	Severe fatigue interfering with ADL	Disabling	--
Radiation dermatitis	Radiation dermatitis	faint erythema or dry desquamation	moderate to brisk erythema or a patchy moist desquamation, mostly confined to skin folds and creases; moderate edema	Moist desquamation other than skin folds and creases; bleeding induced by minor trauma or abrasion	skin necrosis or ulceration of full thickness dermis; spontaneous bleeding from involved site	Death
Dysphagia	Dysphagia	Symptomatic, able to eat regular diet	Symptomatic and altered eating/swallowing (e.g. altered dietary habits, oral supplements); IV fluids indicated <24 hrs	Symptomatic and severely altered eating/swallowing (e.g., inadequate oral caloric or fluid intake); IV fluids, tube feedings, or TPN indicated ≥24 hrs	Life-threatening consequences (e.g., obstruction, perforation)	Death
Fibrosis-deep connective tissue	Fibrosis-deep connective tissue	Increased density, "spongy" feel	Increased density with firmness or tethering	Increased density with fixation of tissue; operative intervention indicated; interfering with ADL	Life-threatening; disabling; loss of limb; interfering with vital organ function	Death
Pneumonitis/Pulmonary Infiltrates	Pneumonitis	Asymptomatic, radiographic findings only	Symptomatic, not interfering with ADL	Symptomatic, interfering with ADL; O2 indicated	Life-threatening; ventilatory support indicated	Death
Dyspnea (Shortness of Breath)	Dyspnea	Dyspnea on exertion, but can walk 1 flight of stairs without stopping	Dyspnea on exertion but unable to walk 1 flight of stairs or 1 city block (0.1 km) without stopping	Dyspnea with ADL	Dyspnea at rest; intubation/ventilator indicated	Death
Hypoxia	Hypoxia	--	Decreased O2 saturation with exercise (e.g. pulse oximeter <88%); intermittent supplemental oxygen	Decreased O2 saturation at rest, continuous oxygen indicated	Life-threatening; intubation or ventilation indicated	Death
Cough	Cough	Symptomatic, non-narcotic medication only indicated	Symptomatic and narcotic medication indicated	Symptomatic and significantly interfering with sleep or ADL	--	--
FEV1	FEV1	90-75% of predicted value	<75-50% of predicted value	<50-25% of predicted value	<25% of predicted value	Death

CONFIDENTIAL

This document is confidential. Do not disclose or use except as authorized.

Pulmonary Fibrosis (radiographic changes)	Pulmonary fibrosis	Minimal radiographic findings (or patchy or bi- basilar changes) with estimated radiographic proportion of total lung volume that is fibrotic of < 25%	Patchy or bi-basilar changes with estimated radiographic proportion of total lung volume that is fibrotic of 25 - <50%	Dense or widespread infiltrates/consolidation with estimated radiographic proportion of total lung volume that is fibrotic of 50 - <75%	Estimated radiographic proportion of total lung volume that is fibrotic is ≥75%; honeycombing	Death
--	-------------------------------	--	--	---	--	--------------

Remark: Fibrosis is usually a “late effect seen >3 months after radiation or combined modality therapy (including surgery). It is thought to represent scar/fibrotic tissue. It may be difficult to distinguish from pneumonitis that is generally seen within 3 months of radiation or combined modality therapy.

CONFIDENTIAL

This document is confidential. Do not disclose or use except as authorized.
